### 2.2.3 Phase II Part 2 Primary Objective and Endpoints

To determine whether hydroxychloroquine added to low dose palbociclib and letrozole can increase the proportion of patients whose tumors achieve complete cell cycle arrest (CCCA, defined as the Ki67  $\leq$  2.7%) comparing T2 to T1 as shown in Figure 2, see Section 5.3.4).

The primary endpoint is the increase in percentage of all patients who achieve CCCA with low dose palbociclib and letrozole (at week 2, time T1) compared to that of low dose palbociclib and letrozole with the addition of HCQ (at 5 weeks, day 29, time T2).

A previously conducted trial of neoadjuvant aromatase inhibitor (anastrozole) plus standard dose palbociclib estimated the CCCA probability to be 44% with aromatase inhibitor alone and powered their study to detect a 50% increase of 44% to 66%. A 26% CCCA probability was seen with anastrozole alone and 86% with the addition of standard dose palbociclib. We will aim for a CCCA reference probability of 50% with low-dose palbociclib + letrozole (T1) and a CCCA probability of 75% with the addition of HCQ (see Section 8 for statistical plan and samples size calculations for the Phase II portion).

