### **3.4 Phase II Component (Window/Neo-adjuvant Cohorts)**

The “window” component of the trial evaluates the combination of pre-operative palbociclib plus letrozole followed by the addition of hydroxychloroquine (HCQ) for postmenopausal patients with Stage I-III estrogen receptor-positive and HER2-negative breast cancer (Figure 2).

Correlative studies using baseline and follow up breast biopsies and blood work are included in the overall research grant. The Phase II portion will assess the change in the percentage of all patients who achieve CCCA when adding HCQ to the palbociclib/letrozole combination.

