### **3.5 Phase II Window/Neo-adjuvant Component – Dose Cohorts (Parts 1 and 2)**

To estimate the dose responsiveness of HCQ in the main outcome measures as stated on Section 2.2.3, two groups will be enrolled at the HCQ levels as shown below:

Dose Level Groups	Number of patients	Hydroxychloroquine dose	Letrozole dose	Palbociclib dose
Part 1	6	400 mg/d p.o.	2.5 mg/d p.o.	75 mg capsule p.o. daily continuously, 28-day cycle
Part 2	30	RP2D		

An initial group of 6 patients (part 1) will be enrolled at an HCQ dose of 400 mg daily sequentially, and then a second group of 30 patients (part 2) will be enrolled at the HCQ dose defined in the Phase I portion as RP2D. The main efficacy endpoint statistical plan is based on the 30 patients enrolled in part 2 as described in Section 8.0.

The dose of palbociclib for both parts 1 and 2 is fixed at a dose of 75 mg orally daily continuously without a break. Letrozole and palbociclib are given for the first 2 weeks, then after the second biopsy (T2), HCQ at the assigned dose will be added. After 4 weeks (2 weeks of HCQ) (T2), the primary endpoint will have been obtained with analysis of the surgical specimen (or research biopsy at that timepoint if additional neoadjuvant endocrine therapy or chemotherapy is indicated as standard of care. Details on dosing and dose adjustments are shown in Sections 6.1.4 and 6.2.3. Using the same population, treatment and biopsy schema, 30 patients will be enrolled for the phase II Stage 2 portion of the trial.

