#### **5.2.3.2 Phase II**

Following the study schema (Figure 2) patients are expected to complete 28 days of study treatment followed by surgery for the “window option”, with an off study visit after surgery, and will be monitored for adverse events up to 30 days after the last dose of study drug.

Patients whose tumors at T1 biopsy show Ki67 > 10% will be required to come off study and per standard of care would typically be recommended to proceed to definitive surgery or standard neoadjuvant chemotherapy. All other patients will continue on study therapy and at T2 (week 5, or day 29), will proceed with definitive surgery or undergo a research biopsy and continue with standard of care neoadjuvant endocrine therapy or chemotherapy as clinically indicated.

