### **Phase II:**

The Phase II portion will be performed in a different population of patients (early stage) in the pre-operative setting. In order to obtain qualitative information about the dose responsiveness of HCQ when added to letrozole and palbociclib, Part 1 of the Phase II portion will enroll 6 patients at an HCQ dose of 400 mg (if in fact, the RP2D is 600 or 800 mg). Following this, Part 2 will be conducted at the RP2D for HCQ based on the primary endpoint of proportion of patients achieving tumoral CCCA, with the formal statistical plan using a 2-stage Simon optimal design and looking to increase the CCCA rate from 50% with low dose palbociclib + letrozole to 75% after the addition of HCQ. This design requires 11 patients in the first stage and 14 patients in the 2nd stage. It would stop after the 1st stage if no more than 6 patients show CCCA by tumor biopsy after HCQ treatment and declared the treatment as promising if at least 17 out of 25 total evaluable patients exhibit CCCA.

This design has alpha = 4%, 81% power, and a probability of 0.73 of terminating after the 1st stage if the true CCCA rate=50%. For the group of patients at the RP2D, we therefore plan a sample size of 30 patients over 12-15 months, accounting for patient dropout (including those with Ki67 >10% at T1). We have a large eligible patient population and have led national accruals in other multi-center neoadjuvant endocrine trials in post-menopausal women (e.g. ALTERNATE Trial). In addition, recent local experience of conducting window of opportunity trials in this setting have demonstrated the feasibility of accrual at a rate of ~2 patients per month. Thus, we expect to achieve accrual goals.

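### The 17-of-25 rule is run after patients with T1 Ki67 >10% are removed, but against a 50% rate stated without that restriction; unless 50% means retained patients, the stated 4% alpha does not hold

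*Combined protocol and SAP*

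**What the plan says.** **Removal.** Section 5.2.3.2: "Patients whose tumors at T1 biopsy show Ki67 > 10% will be required to come off study". Section 3.6 requires four full weeks of therapy and interpretable Ki67 at T0, T1 and T2, so these patients are not evaluable. Section 3.7 replaces non-evaluable Phase II patients. Section 8.0 describes the 30-patient sample as "accounting for patient dropout (including those with Ki67 >10% at T1"). Section 3.8 splits the 30 into 25 needed and 5 expected dropouts, and adds that replaced patients are not counted in that total.

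**Decision rule.** Section 8.0 stops after stage 1 if no more than 6 of 11 patients show CCCA, and otherwise "declared the treatment as promising if at least 17 out of 25 total evaluable patients exhibit CCCA". The stated properties are alpha 4%, power 81% and a 0.73 probability of early stopping at a true rate of 50%.

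**Reference rate.** Section 2.2.3: "We will aim for a CCCA reference probability of 50% with low-dose palbociclib + letrozole (T1"). Section 8.0 repeats it: "looking to increase the CCCA rate from 50% with low dose palbociclib + letrozole to 75% after the addition of HCQ". Neither place limits the 50% or the 75% to patients who pass the T1 check.

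**Endpoint population.** Section 2.2.3: "The primary endpoint is the increase in percentage of all patients who achieve CCCA". Section 3.4: "The Phase II portion will assess the change in the percentage of all patients who achieve CCCA when adding HCQ".

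**The concern.** The removal is not random loss. It selects on the endpoint variable, and it takes out only patients who are failures on the backbone at T1. The patients who remain have a higher CCCA rate before HCQ has done anything. If the 50% describes everyone at T1, the rule compares a selected group with a reference for an unselected one.

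This is the only formal go/no-go rule in the trial, in a single-arm design with a fixed external reference. The mismatch acts in one direction at both looks: it makes a promising result easier to reach, and it makes the stage 1 futility stop less likely when HCQ adds nothing.

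**Working it through.** **Inputs.** From 8.0: stage sizes 11 and 14; stop at ≤6/11; promising at ≥17/25; rates 50% and 75%. From 2.2.3: CCCA is Ki67 ≤2.7%, so T1 Ki67 >10% always means non-CCCA at T1. From 3.8: 30 enrolled, 5 of them expected dropouts from all causes. Not in the documents: the share q removed for T1 Ki67 >10%. It is varied below as k of 30.

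**Step 1. Reproduce the plan.** For a true rate p,

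Reject(p) = Σ over x = 7..11 of Bin(x; 11, p) × P(Bin(14, p) ≥ 17 − x), and Stop(p) = P(Bin(11, p) ≤ 6).

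At p = 0.50 the five terms are:

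| x | Bin(x; 11, 0.5) | P(Bin(14, 0.5) ≥ 17 − x) | product |
|---|---|---|---|
| 7 | 0.1611 | 0.0898 | 0.0145 |
| 8 | 0.0806 | 0.2120 | 0.0171 |
| 9 | 0.0269 | 0.3953 | 0.0106 |
| 10 | 0.0054 | 0.6047 | 0.0032 |
| 11 | 0.0005 | 0.7880 | 0.0004 |

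The sum is 0.0458. Stop(0.50) = 0.7256 and Reject(0.75) = 0.8005. The stated 0.73 reproduces. Exact alpha is 4.6% against the stated 4%, and power is 80.1% against the stated 81%. The design still meets 5% and 80%.

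**Step 2. No-effect rate after removal.** Let 50% be the all-patient T1 rate. All CCCA patients are retained and the denominator shrinks by q. If CCCA status is the same at T2 as at T1 without HCQ, and other losses are random, the no-effect rate among analysed patients is p = 0.50/(1 − q), with q = k/30.

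| k of 30 removed | p | alpha of the stated rule | early stop, no effect |
|---|---|---|---|
| 0 | 0.500 | 4.6% | 0.73 |
| 1 | 0.517 | 6.5% | 0.69 |
| 2 | 0.536 | 9.1% | 0.64 |
| 3 | 0.556 | 12.6% | 0.59 |
| 5 | 0.600 | 24.0% | 0.47 |

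The last row is the extreme in which all five planned dropouts are T1 removals. Alpha passes 5% at q of about 0.9% and 10% at about 7.7%.

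**Step 3. The other reading.** If 50% is the rate among retained patients, p stays at 0.50 and alpha stays at 4.6%. The implied all-patient T1 rate is then 0.50 × (1 − k/30): 46.7%, 45.0% or 41.7% for k = 2, 3 or 5.

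**Step 4. Changing only the final cut-off.** For k = 2 (null 0.536), ≥18/25 with the same stage 1 gives alpha 4.4% and power 70% at 75%. For k = 3 (null 0.556), ≥19/25 gives alpha 2.8% and power 55% at 75%. Early stopping stays at 0.64 and 0.59, because it depends only on the ≤6/11 boundary.

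**The case against.** The strongest reply is that Section 8.0 can be read with 50% as the null for the evaluable set. It counts successes among evaluable patients, attaches the stopping probability to a true rate of 50%, and mentions the T1 losses straight afterwards, so the author knew of the removal when fixing 25. On that reading there is no inflation. This stands as a possible reading. It does not settle the matter: 2.2.3 ties the 50% to T1, before anyone is removed, and 2.2.3 and 3.4 speak of all patients. That phrase could loosely mean all evaluable patients, but the plan never says so.

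A second reply is that 50% is a chosen benchmark, not a measured rate. That is fair. The prior-trial rates observed in 2.2.3 (26% on anastrozole alone, 86% with standard-dose palbociclib) do not yield 50% for either population. A chosen benchmark still has to be attached to a population before an error rate can be quoted for it.

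A third reply is that the share removed is unknown and the trial is an early single-arm study, so a small excess alpha may matter little. The first part is correct, and the table is therefore illustrative.

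A reader might infer that the true alpha is 24%. The documents do not support that: it needs every planned dropout to be a T1 removal, while Section 3.8 gives five as an all-cause figure. Nor is five a ceiling on removals, since replacements come on top. A reader might also infer that the off-study rule is at fault. It is not; only the match between the analysed set and its null is in question.

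**Conclusion.** The point holds in conditional form. As worded, the plan tests a set from which T1 failures have been removed against a rate stated without that restriction, and on that plain reading the stated 4% alpha does not hold. The mechanism is in the text. The size is not, because q is undocumented: 6.5% to 12.6% for 1 to 3 of 30 removed is an illustration. It rests on 50% being the all-patient T1 rate, on CCCA status not changing between T1 and T2 without HCQ, and on other losses being random.

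If the sponsor meant 50% for retained patients, the error rate is not inflated. What remains is an unstated population, endpoint wording that does not fit it, and stated figures of 4% and 81% where the exact values are 4.6% and 80.1%. It would go too far to say that inflation is established. What is established is that the plan does not fix the population on which its quoted alpha depends. A correction is needed on either reading.

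**What to change.** Leave the T1 off-study rule unchanged. In 2.2.3, 3.6, 3.7 and 8.0, name one primary analysis population and state that both the 50% and the 75% refer to it. Then:

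- **If 50% is for retained patients:** say so, give the basis, drop the all-patients wording, and restate alpha as 4.6% and power as 80.1%. This costs wording only.
- **If 50% is the all-patient rate:** project q, raise the null to 0.50/(1 − q), and re-derive both the stage 1 and the final boundaries. Changing only the final cut-off leaves the weakened stage 1 stop in place. Restate alpha, power and early stopping, and name the power loss at 75%; with 25 patients and stage 1 unchanged, power is already down to 70% for 2 removed and 55% for 3.

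In either case report the number removed at T1, the CCCA rate counting removed patients as non-CCCA (sensitivity analysis), and, as supportive, the paired T1 and T2 CCCA rates in the same retained patients. The paired comparison uses biopsies already required and needs no external 50%.

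Counting removals as failures in the primary rule (continue at ≥7/11, promising at ≥20/30) is an option for the sponsor, not a required change. It gives alpha 4.0%, and power 82.6% if 75% is the all-patient rate. If 75% describes continuing patients only, the all-patient rate is 0.75 × (1 − k/30), that is 70%, 67.5% or 62.5% for 2, 3 or 5 removed, and power falls to 65%, 54% or 33%. It also changes the question to success of the whole treatment sequence.

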## **8.1 IND Office Reporting**

The Investigator is responsible for completing toxicity/efficacy summary reports and submitting them to the IND office

Medical Affairs and Safety Group for review. These should be submitted as follows:

- Phase I:

After the first 3 evaluable patients, complete 1 cycle of study treatment, and every 3 evaluable patients thereafter, IND Office approval must be obtained prior to advancing/changing dose levels.

- Phase II:

After the first 6 evaluable patients complete 4 weeks of study treatment, and every 6 patients thereafter.

A copy of the cohort summary should be placed in the Investigator's Regulatory Binder under "sponsor correspondence".

## **9.0 INSTITUTIONAL REVIEW, CONSENT, MEDICAL MONITORING AND RECORD-KEEPING AND SAFETY MONITORING**

### **9.1 Informed Consent**

The informed consent documents must be signed by the subject or the subject's legally authorized representative before his or her participation in the study. The case history for each subject shall document that informed consent was obtained prior to participation in the study. A copy of the informed consent document must be provided to the subject or the subject's legally authorized representative. If applicable, it will be provided in a certified translation of the local language.

Signed consent forms must remain in each subject's study file and must be available for verification by study monitors at any time.

## **9.2 Institutional Review Board Approval**

This protocol, the informed consent document, and relevant supporting information must be submitted to the IRB for review and must be approved before the study is initiated. The study will be conducted in accordance with FDA, applicable national and local health authorities, and IRB requirements.

The Principal Investigator is responsible for keeping the IRB apprised of the progress of the study and of any changes made to the protocol as deemed appropriate, but in any case, the IRB must be updated at least once a year. The Principal Investigator must also keep the IRB informed of any significant AEs.

Investigators are required to promptly notify their respective IRB of all adverse drug reactions that are both serious and unexpected. This generally refers to SAEs that are not already identified in the Investigator's Brochure and that are considered possibly or probably related to the molecule or study drug by the investigator. Some IRBs may have other specific AE requirements to which investigators are expected to adhere. Investigators must immediately forward to their IRB any written safety report or update provided by Pfizer (e.g., IND safety report, Investigator's Brochure, safety amendments and updates, etc.).

## **9.3 Confidentiality**

Patient medical information obtained by this study is confidential and may be disclosed to third parties only as permitted by the ICF (or separate authorization to use and disclose personal health information) signed by the patient or unless permitted or required by law. Medical information may be given to a patient's personal physician or other appropriate medical personnel responsible for the patient's welfare for treatment purposes. Data generated by this study must be available for inspection upon request by representatives of the FDA and other regulatory agencies as applicable.

## **9.4 Study Medical Monitoring Requirements**

This clinical research study will be monitored internally (by the PI) and externally (by the MDACC IRB). In terms of internal review, the PI will continuously monitor and tabulate AEs. Appropriate reporting to the MDACC IRB will be made. The PI of this study will also continuously monitor the conduct, data, and safety of this study to ensure that:

- Interim and safety analyses occur as scheduled,
- Stopping rules for toxicity and/or response are met,
- Risk/benefit ratio is not altered to the detriment of the subjects,
- Appropriate internal monitoring of AEs and outcomes is done,
- Over-accrual does not occur,
- Under-accrual is addressed with appropriate amendments or actions, and
- Data are being appropriately collected in a reasonably timely manner.

Routine monitoring will be carried out via a periodic team conference among investigators during which toxicity data, including all SAEs, will be reviewed and other issues relevant to the study such as interim assessment of accrual, outcome, and compliance with study guidelines, will be discussed.

Monitoring will be carried out on an ongoing basis. The severity, relatedness, and whether or not the event is expected will be reviewed. Data will be housed and analyzed on a Redcap database using our institutional and Departmental protocols for data entry and verification.

## **9.5 Data Collection**

The study coordinator and investigators are responsible for ensuring that the eligibility checklist is completed in a legible and timely manner for every patient enrolled in the study, and that data are recorded on the appropriate forms and in a timely manner. Any errors on source data should be lined through, but not obliterated, with the correction inserted, initialed, and dated by the study coordinator or PI. All source documents will be available for inspection by the FDA and the MD Anderson IRB.

## APPENDIX A - Palbociclib (Ibrance) Highlights of Prescribing Information

### HIGHLIGHTS OF PRESCRIBING INFORMATION

These highlights do not include all the information needed to use IBRANCE safely and effectively. See full prescribing information for IBRANCE.

**IBRANCE® (palbociclib) capsules, for oral use Initial U.S. Approval: 2015**

#### ----- RECENT MAJOR CHANGES -----

Indications and Usage (1) 03/2017

Dosage and Administration (2.1, 2.2) 03/2017

Warnings and Precautions (5.1, 5.2) 03/2017 Warnings and Precautions, Pulmonary Embolism (5)  
Removed 03/2017

#### ----- INDICATIONS AND USAGE -----

IBRANCE is a kinase inhibitor indicated for the treatment of hormone receptor (HR)-positive, human epidermal growth factor receptor 2

(HER2)-negative advanced or metastatic breast cancer in combination with:

- an aromatase inhibitor as initial endocrine based therapy in postmenopausal women; or
- fulvestrant in women with disease progression following endocrine therapy. (1)

#### ----- DOSAGE AND ADMINISTRATION -----

IBRANCE capsules are taken orally with food in combination with an aromatase inhibitor or fulvestrant. (2)

- Recommended starting dose: 125 mg once daily taken with food for 21 days followed by 7 days off treatment. (2.1)
- Dosing interruption and/or dose reductions are recommended based on individual safety and tolerability. (2.2)

#### ----- DOSAGE FORMS AND STRENGTHS -----

Capsules: 125 mg, 100 mg, and 75 mg. (3)

#### ----- CONTRAINDICATIONS -----

None. (4)

**----- WARNINGS AND PRECAUTIONS -----**

- Neutropenia: Monitor complete blood count prior to start of IBRANCE therapy and at the beginning of each cycle, as well as on Day 15 of the first 2 cycles, and as clinically indicated. (2.2, 5.1)
- Embryo-Fetal Toxicity: IBRANCE can cause fetal harm. Advise patients of potential risk to a fetus and to use effective contraception. (5.2, 8.1, 8.3)

**----- ADVERSE REACTIONS -----**

Most common adverse reactions (incidence  $\geq 10\%$ ) were neutropenia, infections, leukopenia, fatigue, nausea, stomatitis, anemia, alopecia, diarrhea, thrombocytopenia, rash, vomiting, decreased appetite, asthenia, and pyrexia. (6)

**To report SUSPECTED ADVERSE REACTIONS, contact Pfizer Inc at [name] or FDA at [name] or [www.fda.gov/medwatch](http://www.fda.gov/medwatch).**

**----- DRUG INTERACTIONS -----**

- CYP3A Inhibitors: Avoid concurrent use of IBRANCE with strong CYP3A inhibitors. If the strong inhibitor cannot be avoided, reduce the IBRANCE dose. (2.2, 7.1)
- CYP3A Inducers: Avoid concurrent use of IBRANCE with strong CYP3A inducers. (7.2)
- CYP3A Substrates: The dose of sensitive CYP3A4 substrates with narrow therapeutic indices may need to be reduced when given concurrently with IBRANCE. (7.3)

**----- USE IN SPECIFIC POPULATIONS -----**

- Lactation: Advise not to breastfeed. (8.2)

**See 17 for PATIENT COUNSELING INFORMATION and  
FDA-approved patient labeling.**

## FULL PRESCRIBING INFORMATION

### 1. INDICATIONS AND USAGE

IBRANCE is indicated for the treatment of HR-positive, HER2-negative advanced or metastatic breast cancer in combination with:

- an aromatase inhibitor as initial endocrine based therapy in postmenopausal women; or
- fulvestrant in women with disease progression following endocrine therapy.

### 2. DOSAGE AND ADMINISTRATION

#### 1. Recommended Dose and Schedule

The recommended dose of IBRANCE is a 125 mg capsule taken orally once daily for 21 consecutive days followed by 7 days off treatment to comprise a complete cycle of 28 days. IBRANCE should be taken with food [see *Clinical Pharmacology (12.3)*].

administer the recommended dose of an aromatase inhibitor when given with IBRANCE. Please refer to the Full Prescribing Information for the aromatase inhibitor being used.

When given with IBRANCE, the recommended dose of fulvestrant is 500 mg administered on Days 1, 15, 29, and once monthly thereafter. Please refer to the Full Prescribing Information of fulvestrant.

Patients should be encouraged to take their dose of IBRANCE at approximately the same time each day.

If the patient vomits or misses a dose, an additional dose should not be taken. The next prescribed dose should be taken at the usual time. IBRANCE capsules should be swallowed whole (do not chew, crush, or open them prior to swallowing). Capsules should not be ingested if they are broken, cracked, or otherwise not intact.

Pre/perimenopausal women treated with the combination IBRANCE plus fulvestrant therapy should be treated with luteinizing hormone-releasing hormone (LHRH) agonists according to current clinical practice standards.

